9.5. Single Reference Safety Document

The local product document will serve as the SRSD during the course of the study, and the investigator will use it to assess all the safety events reported to Pfizer Safety during the course of this study.

The investigator must use the SRSD for prescribing purposes and guidance.

10. PLANS FOR DISSEMINATING AND COMMUNICATING STUDY RESULTS

For the first 2 years, 6-month reports will be submitted to the MFDS (i.e., Reports 1-1, 1-2, 2-1, and 2-2). Thereafter, data collected in the 3rd, 4th, and 5th year will be reported to the MFDS annually. The final study report (i.e., re-examination report) will be submitted to the MFDS in the 6th year to include all data collected during the whole study period (see Section 4).

COMMUNICATION OF ISSUES

In the event of any prohibition or restriction imposed (e.g., clinical hold) by an applicable competent authority in any area of the world, or if the investigator becomes aware of any new information which might influence the evaluation of the benefits and risks of Duavive tab. 0.45 mg/20 mg, it should be reported to Pfizer immediately.

In addition, the investigator must inform Pfizer immediately of any urgent safety measures taken by the investigator to protect the subjects against any immediate hazard, and of any serious breaches of this non-interventional study protocol that the investigator becomes aware of.

ANNEX 1. LIST OF STAND ALONE DOCUMENTS

None.

ANNEX 2. ADDITIONAL INFORMATION

Not applicable.

1 AMENDMENTS FROM PREVIOUS VERSION(S)

Version	Date of Revision	Reason for change	Author name
Version 1.0	04-APR-2016	1st Version	PPD
Version 2.0	08-SEP-2016	Add analysis of hormone therapy related to menopause before administration of Duavive Tab.	PPD
Version 3.0	TBD	
 1) Addition of calculation method of 'Duration of disease' 2) Addition of AE listings 3) Addition of SAE/SADR, unexpected AE/unexpected ADR by preferred terms according to the frequency categories in the approved local label 4) Addition of Basic Results Tables 5) Change of AE coding dictionary 	PPD

2 INTRODUCTION

Note: In this document any text taken directly from the protocol is *italicized*.

Duavive tab. is a tissue selective estrogen complex (TSEC) made by combining bazedoxifene, a selective estrogen receptor modulator (SERM), with conjugated estrogen (CE). Duavive tab. was approved by the Ministry of Food and Drug Safety on 25 July 2014 for the treatment for moderate to severe vasomotor symptoms associated with menopause and the prevention of post-menopausal osteoporosis in women with a uterus¹.

As required for new medications approved by the MFDS, safety and efficacy information should be provided for a minimum of 600 subjects treated in the setting of routine practice during 6 years following the approval (25 July 2014 to 24 July 2020). This non-interventional post-marketing surveillance (PMS) study is an obligation to the MFDS.

Background information on Duavive tab. can be obtained from the current version of the local product document, which is the single reference safety document (SRSD) for information relating to Duavive tab. in this study.

2.1 STUDY DESIGN

This is an open-label, non-comparative, non-interventional, prospective, and multi-center study conducted in Korean health care centers by accredited physicians (i.e., investigators). The study will be conducted with those subjects administered with Duavive tab. as a part of routine treatment who comply with the local labeling. Duavive tab. will be administered according to the “Dosage and Administration” specified in the approved

local product document. Since this study intends to observe routine treatment situation, there is no visit or activity mandated by this study. The investigator will collect data by observing enrolled subjects and record the information on each subject's case report form (CRF).

Study population

At least 600 subjects will be enrolled in about 20 study sites in this study based on the MFDS re-examination regulation. Each investigator will sequentially enroll all female subjects who are administered Duavive tab. for the first time according to the local product document after the start of the study at a study site and who agree to participate in this study by signing the data privacy statement until the total requested cases per site are collected for this study.

[Inclusion criteria]

To be eligible to enroll in this study, a patient will have to meet the following inclusion criteria:

- 1) Women who have been administered Duavive tab. for the first time according to the current local labeling (indications, administration and dosage) of Duavive tab. after the start of the study at a study site*

Indications

This drug is used to treat the following diseases in women with a uterus for:

- 1) Treatment for moderate to severe vasomotor symptoms associated with menopause*
- 2) Prevention of post-menopausal osteoporosis*

Administration and Dosage

- 1) Treatment for moderate to severe vasomotor symptoms associated with menopause
The recommended dosage is one DUAVIVE tablet daily.*
- 2) Prevention of post-menopausal osteoporosis
The recommended dosage is one DUAVIVE tablet daily.*
- 3) General dosing information
Take DUAVIVE once daily, without regard to meals. Tablets should be swallowed whole. They should not be chewed or crushed.*
- 4) Recommendation for Calcium or Vitamin D supplementation
Women taking DUAVIVE for prevention of post-menopausal osteoporosis should add supplemental calcium and/or vitamin D to their diet if daily intake is inadequate.*
- 5) Administration Instructions for Missed Doses
If a dose of DUAVIVE is missed, instruct patients to take it as soon as remembered unless it is almost time for the next scheduled dose. They should not*

take two doses at the same time.

- 2) *Post-menopausal women*
- 3) *Women who have consented to participate in this study by signing the data privacy statement*

[Exclusion criteria]

Patients, who meet at least one of the following criteria, will not be included in the study:

- 1) *Women who have deviated from local labeling in taking this drug*
- 2) *Women with undiagnosed abnormal uterine bleeding*
- 3) *Women with known, suspected, or past history of breast cancer*
- 4) *Women with known or suspected estrogen-dependent neoplasia*
- 5) *Women with active deep venous thrombosis, pulmonary embolism, or history of these conditions*
- 6) *Women with active arterial thromboembolic diseases (e.g.: stroke, myocardial infarction) or history of these conditions*
- 7) *Women taking progestins, estrogens, or estrogen agonist/antagonists*
- 8) *Women with hypersensitivity (e.g.: anaphylaxis, angioedema) to estrogens, bazedoxifene, or any ingredients*
- 9) *Women with known hepatic impairment or diseases*
- 10) *Women with known protein C, protein S, or antithrombin deficiency or other known thrombophilic disorders*
- 11) *Pregnancy, women who may become pregnant and nursing mothers*
- 12) *Patients with hereditary problems of galactose intolerance, Lapp lactase deficiency or glucose-galactose malabsorption*

2.2 STUDY OBJECTIVES

In this study, the safety and efficacy of Duavive tab. 0.45 mg/20 mg will be observed under the actual condition of use.

The objectives of this post-marketing surveillance are as follows:

- 1) *To observe the safety and efficacy profile of Duavive tab. 0.45 mg/20 mg in the Korean subjects.*
- 2) *To identify the factors that can have an effect on the safety and efficacy profile of Duavive tab. 0.45 mg/20 mg in the Korean subjects.*

3 INTERIM AND FINAL ANALYSES

This Statistical Analysis Plan (SAP) details the analyses and outputs to be produced for the interim and final analyses.

For the first 2 years, 6-month reports will be submitted to the MFDS (i.e., Reports 1-1, 1-2, 2-1, and 2-2). Thereafter, data collected in the 3rd, 4th, and 5th year will be reported to the MFDS annually. The final study report (i.e., re-examination report) will be submitted to the MFDS in the 6th year to include all data collected during the whole study period. The first interim analysis will be performed once this SAP is finalized.

All analyses outlined in this SAP, except for those described below, will be performed for each interim analysis for the periodic report annually.

- Type of medical history (Past disease, Present disease)
- Type of concomitant medications
- Type of Hormone therapy related to menopause before administration of Duavive Tab.
- SAE/SADR, unexpected AE/unexpected ADR by preferred terms according to the frequency categories in the approved local label
- Basic Results Tables

4 HYPOTHESES AND DECISION RULES

Not Applicable

5 ANALYSIS SETS/ POPULATIONS

All subjects entered into this study will be evaluated as to whether they are eligible to be in the Safety Analysis Set and the Effectiveness Analysis Set.

All subjects excluded from the Safety Analysis Set will be accounted for as part of the subject accounting in the Clinical Study Report. Any adverse events reported for subjects excluded from the Safety Analysis Set will also be described.

5.1 SAFETY ANALYSIS SET

Subject who have been administered Duavive tab. at least once and completed follow up will be included in the safety analysis set.

The following exclusions from the Safety Analysis Set are to ensure that the subjects who are not providing data to the analyses but have some record of treatment do not over-inflate the denominator for the analyses.

The following cases are excluded from the safety analysis set:

- 1) Subjects who were enrolled in the study prior to the starting date of the study period at the site
- 2) Subjects who didn't receive Duavive tab.

- 3) Follow-up failure: Subjects for whom adverse event status (Adverse Events status is unknown or missing in the CRF) could not be established
- 4) Subjects who violated inclusion/exclusion criteria (see section 2.1)

Statistical analysis on safety parameters will be performed on the safety analysis set.

5.2 EFFECTIVENESS ANALYSIS SET

The effectiveness analysis set is a subset of the safety analysis set.

The following cases are excluded from the effectiveness analysis set:

- 1) Subjects excluded from safety analysis set listed in section 5.1
- 2) Subjects whose items on the clinical response of “Treatment for moderate to severe vasomotor symptoms associated with menopause” in effectiveness evaluation on the CRF are not completed[†]
- 3) Subjects whose items on the clinical response of “Prevention of post-menopausal osteoporosis” in effectiveness evaluation on the CRF are not completed[‡]
- 4) Subjects who are assessed as “unevaluable” on the clinical response of “Treatment for moderate to severe vasomotor symptoms associated with menopause” in effectiveness evaluation on the CRF[†]
- 5) Subjects who are assessed as “unevaluable” on the clinical response of “Prevention of post-menopausal osteoporosis” in effectiveness evaluation on the CRF[‡]

[†] Only if main indication is “Treatment for moderate to severe vasomotor symptoms associated with menopause”

[‡] Only if main indication is “Prevention of post-menopausal osteoporosis”

Statistical analysis on effectiveness parameters will be performed on the effectiveness analysis set.

6 ENDPOINTS AND COVARIATES

6.1 SAFETY ENDPOINTS

Adverse Event Occurrence

6.2 EFFECTIVENESS ENDPOINT(S)

- 1) Treatment for moderate to severe vasomotor symptoms associated with menopause: Investigator’s judgment on the improvement of the symptom recorded during the treatment

2) Prevention of post-menopausal osteoporosis:

- The investigator's evaluation of preventive effect based on this information.
- Laboratory test results (if any)
 - X-ray examination
 - Bone density test record (Bone mineral density)
 - Other blood test record related to resorption of bone and osteogenesis (Biochemical marker of bone turnover)

7 HANDLING OF MISSING VALUES

No imputation of missing data will be performed. Missing or incomplete dates will be excluded from the analysis.

8 STATISTICAL METHODOLOGY AND STATISTICAL ANALYSES

8.1 STATISTICAL METHODS

All test statistics will be the results of two-sided tests with the statistical significant level of 0.05.

8.1.1 Analysis for Continuous Data

Descriptive summary statistics for continuous variables will include the following:

- number of subjects (n), mean, standard deviation (SD), median, minimum and maximum.

8.1.2 Analysis for Categorical Data

Descriptive statistics for categorical variables will be given as frequencies and percentages. The denominator will be the number of subjects included either in the safety analysis set or effectiveness analysis set depending on where the analysis is presented.

Where appropriate, the percentages will be presented with a corresponding 95% confidence interval. Comparisons between subcategories of each baseline characteristic will be made using chi-square test or Fisher's exact test. Test statistics include p-value. When more than 20% of expected frequency of the cell count is less than 5, Fisher's exact test should be used instead of chi-square test.

8.2 STATISTICAL ANALYSES

8.2.1 Safety Analyses

8.2.1.1 Baseline Characteristics

Baseline characteristics for this study are defined as follows:

- Continuous measurements will be presented Mean (SD) :
 - Age
 - Duration of disease[†]
 - Total administration period of Duavive tab.[‡]
- Categorized measurements will be presented n(%) :
 - Main indication (Treatment for moderate to severe vasomotor symptoms associated with menopause, Prevention of post-menopausal osteoporosis, both)
 - Geriatric status (<65 years, ≥65 years)
 - Age (<50 years, ≥50 years and ≤59 years, ≥60 years and ≤69 years, ≥70 years*)
 - Allergy history (Yes, No)
 - Duration of disease[†] (<3 months, ≥3 months and <6 months, ≥6 months*)
 - Medical history (Past disease, Present disease/Yes, No)
 - Total administration period of Duavive tab. (<3 months, ≥3 months and <6 months, ≥6 months*)
 - Long-term administration (<22 weeks, ≥22 weeks of total administration period of Duavive tab.)
 - Kidney disorder (Yes, No)
 - Liver disorder (Yes, No)
 - Concomitant medication (Yes, No)
 - Hormone therapy related to menopause before administration of Duavive Tab. (Yes, No)

[†] Only if main indication is “Treatment for moderate to severe vasomotor symptoms associated with menopause”

Duration of disease (months) = (number of years after diagnosis)×12+(number of months after diagnosis)

[‡] Total administration period of Duavive tab.= Sum of each administration period

: Each administration period = (Administration end date) – (Administration start date) + 1

If the medication is being continued at the completion of the study, administration end date is replaced with effectiveness evaluation date at last visit.

* The categories can be altered depending on the data distribution.

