7.3.1.1. Collection of Adverse Events Data

Please refer to Section 9 for the definition of adverse event (AE) and serious adverse event (SAE).

All AEs occurring within the adverse event reporting period will be recorded on the CRF by the investigator after the investigator reviews each subject's medical data.

Check either 'Yes' or 'No' in the AE section of CRF. If 'Yes', record the details.

- Adverse event: Record the pertinent name of the AE. Record the name of the AE by selecting an appropriate term among the Preferred Terms of the MedDRA. If no appropriate terms are found, use an optimal term listed in the Medical Terminology Dictionary (Korean Medical Society).
- Date of onset: Record the onset date of the AE. Record an approximate date if the actual date is unknown.
- Severity: Severity of the AE must be evaluated according to the following categories:
 - Mild: Not causing any significant problem to the subject. Administration of medicinal product continues without dose adjustment.
 - Moderate: Causing a problem that does not interfere significantly with usual activities or the clinical status. Dose of the medicinal product is adjusted or other therapy is added due to the AE.
 - Severe: Causing a problem that interferes significantly with usual activities or the clinical status. The medicinal product is discontinued due to the AE.
- Measures taken in relation to Duavive tab.: Select among the following options:
 - Permanently discontinued
 - Temporarily discontinued or delayed
 - Dose reduced
 - Dose increased
 - No change
 - Not applicable
- Other measures: Other measure taken after the onset of an adverse event is to be indicated in the following pertinent number and its content is to be described.
 - Prescription of treatment drug (Record the details in the Concomitant Medications section)
 - Other (Provide details)
 - Untreated
- Seriousness: In response to the question 'Is any of the seriousness criteria applicable?', check either 'Yes' or 'No'. If 'Yes', enter an applicable number among the definitions of serious adverse events. When a death has been caused, enter the date of death.
- Outcome: The evaluation of outcome will include: Record the date of recovery in case of 'Recovered' or 'Recovered with sequelae'.

- Recovered
 - Recovered with sequelae
 - Recovering
 - Not recovered
 - Unknown

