8.2.1.3 Adverse Events by Baseline Characteristics

The following will be presented for AEs, split by the baseline characteristics using the safety analysis set:

- The number of subjects to whom AE occurred and the number of AEs will be calculated.
- The proportion of subjects to whom AE occurred and its 95% confidence interval will be estimated and compared between subcategories of each baseline characteristic using chi-square test or Fisher's exact test. When more than 20% of expected frequency of the cell count is less than 5, Fisher's exact test should be used instead of chi-square test.
- Adverse event presentations will be split by the following baseline characteristics (See Categorized measurements of Section 8.2.1.1)

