8.2.2 Effectiveness Analyses

Final effectiveness will be analyzed based on the evaluation of investigator for clinical response. Effectiveness analyses will be conducted for each indication. Because both indications can be selected, subjects can include in effectiveness analysis in duplicate.

- 1) Treatment for moderate to severe vasomotor symptoms associated with menopause:

Subjects who were assessed as ‘improved’ in “effectiveness evaluation” would be considered as “Effectiveness” and ‘no change’, ‘aggravated’ in “effectiveness evaluation” would be considered as “Ineffectiveness”. The effectiveness rate at last visit, which is defined as the proportion of subjects classified as ‘effectiveness’ in the final effectiveness evaluation, will be estimated with its 95% confidence interval.

For at last visit, the effectiveness rate according to the baseline characteristics listed in categorized measurements of section 8.2.1.1 (except for “Main indication” item) will be analyzed. Chi-square test or Fisher’s exact test will be used for comparing between subcategories of each baseline characteristic. When more than 20% of expected frequency of the cell count is less than 5, Fisher’s exact test should be used instead of chi-square test.

The frequency and percentage of clinical response evaluation at 3 months (± 2 weeks), 6 months (± 2 weeks), last visit (‘Effectiveness (improved)’, ‘Ineffectiveness (no change, aggravated)’ will be summarized.

- 2) Prevention of post-menopausal osteoporosis:

Subjects who were assessed as ‘effective in prevention’ in “effectiveness evaluation” would be considered as “effectiveness” and ‘ineffective in prevention’ in “effectiveness evaluation” would be considered as “ineffectiveness”. The effectiveness rate at last visit, which is defined as the proportion of subjects classified as ‘effectiveness’ in the final effectiveness evaluation, will be estimated with its 95% confidence interval.

For at last visit, the effectiveness rate according to the baseline characteristics listed in categorized measurements of section 8.2.1.1 (except for “Main indication” item) will be analyzed. Chi-square test or Fisher’s exact test will be used for comparing between subcategories of each baseline characteristic. When more than 20% of expected frequency of the cell count is less than 5, Fisher’s exact test should be used instead of chi-square test.

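### The SAP tests time on drug as a baseline factor, so adverse-event and effectiveness differences can appear with no duration effect

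*SAP*

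**What the plan says.** SAP 8.2.1.1 defines the baseline characteristics. Two of the categorized items are durations of treatment: "Total administration period of Duavive tab. (<3 months, ≥3 months and <6 months, ≥6 months" and "Long-term administration (<22 weeks, ≥22 weeks of total administration period of Duavive tab". A footnote fixes the end date for women still on drug: "If the medication is being continued at the completion of the study, administration end date is replaced with effectiveness evaluation date at last visit".

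Both items then enter tests. For AEs, SAP 8.2.1.3 states: "The proportion of subjects to whom AE occurred and its 95% confidence interval will be estimated and compared between subcategories of each baseline characteristic", and refers back to all categorized items. For each indication, SAP 8.2.2 analyses "For at last visit, the effectiveness rate according to the baseline characteristics listed in categorized measurements of section 8.2.1.1" and omits only the main indication. SAP 8.1 adds: "All test statistics will be the results of two-sided tests with the statistical significant level of 0.05". No landmark, fixed AE window or person-time method is given.

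On context, SAP 4 has no hypotheses or decision rules, and protocol 7.7.2 describes a mainly descriptive evaluation whose subgroup analyses look for factors affecting safety and efficacy, which is the second study objective.

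**The concern.** A baseline factor is fixed before any outcome can occur. These two are settled by what happens during follow-up, partly by the outcome itself.

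For AEs, two biases oppose each other. A woman observed for 6 months has about twice the time for an AE as one observed for 3. Against that, an AE that ends treatment puts her in a short-duration group. The protocol's own severity scale (7.3.1.1) makes that link for severe events: "The medicinal product is discontinued due to the AE".

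For effectiveness, the plausible bias runs one way. If non-improvers continue less often, the group reaching 22 weeks is enriched with improvers. The reverse needs improvers to stop more often. Women stopping before 3 months are mostly unevaluable (protocol 7.3.2.1, SAP 5.2), so this concerns women with a 3-month rating.

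A small p-value in either row could be read as long-term use being safer, riskier or more effective, and so be taken as an answer to the second objective.

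**Working it through.** The plan has no AE rate, stopping rate or effectiveness rate to reproduce.

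**Inputs from the documents.** At least 600 women (protocol 7.5); observation to 3 months, with an additional evaluation at 6 months, each ± 2 weeks (protocol 7.2.4); AE reporting to 28 days after last dose (protocol 9.2); two-sided 0.05 (SAP 8.1); chi-square, or Fisher when more than 20% of expected counts are below 5 (SAP 8.1.2).

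**Hand check of the two AE directions.** Assume every woman has the same AE hazard, 2% per month. With a 30.44-day month, 22 weeks is 154/30.44 = 5.06 months.
- No AE stops treatment: risk is 1 − exp(−0.02 × 3) = 5.8% over 3 months and 1 − exp(−0.02 × 6) = 11.3% over 6.
- Every AE stops treatment: a woman reaches 22 weeks only if AE-free, so she can have an AE only between 5.06 and 6 months, with risk 1 − exp(−0.02 × 0.94) = 1.9%. All earlier AEs fall in the short group.

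**AE simulation.** Assumed: n = 600; constant hazard, hence no duration effect; other stopping 5% per month; 40% followed to 6 months and the rest to 3, each ± 14 days; 1000 trials per cell. Rejection (%) of the 22-week test, by share of AEs that stop treatment:

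| AEs per month | 0% | 25% | 50% | 75% | 100% |
|---|---|---|---|---|---|
| 1% | 46 | 14 | 5 | 21 | 73 |
| 2% | 71 | 22 | 4 | 43 | 95 |
| 5% | 97 | 44 | 6 | 72 | 100 |

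At 2% per month the AE percentages (<22 / ≥22 weeks) are 5.3/11.2 when no AE stops treatment, 7.3/6.7 at half and 9.3/1.8 when all do. In this base case, at 25% stopping or less, at least 96% of rejections show more AEs at ≥22 weeks; at 75% or more, virtually all show the opposite. The three-group row at 2% rejects in 54/10/15/67/99%.

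Sensitivity of the 22-week row at 2% per month:

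| Change | 0% | 25% | 50% | 75% | 100% |
|---|---|---|---|---|---|
| AEs in 28 days after last dose also count | 62 | 18 | 6 | 34 | 85 |
| Front-loaded (2× hazard in month 1, 0.3× after) | 18 | 5 | 19 | 68 | 99 |
| Hazards differ between women, gamma variance 2 | 65 | 17 | 7 | 52 | 97 |
| Gamma variance 4 | 55 | 11 | 10 | 56 | 97 |
| 20% followed to 6 months | 58 | 24 | 6 | 9 | 45 |
| 60% followed to 6 months | 77 | 13 | 22 | 88 | 100 |
| Other stopping 2% per month | 68 | 17 | 9 | 62 | 99 |
| Other stopping 10% per month | 71 | 29 | 5 | 18 | 81 |

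The Monte Carlo standard error is at most 1.6 points, but separately coded runs of the base model differed by up to about 9 points, so the figures are approximate. In a related model with 28 days of AE capture, a factor truly fixed at baseline rejected in 4.4–5.7% of trials. The test is sound; the grouping is the fault.

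**Effectiveness.** Assume 400 women with a 3-month rating, 80% improved (320 against 80), ratings unchanged afterwards, and 45% of improvers reaching 22 weeks (320 × 0.45 = 144).

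| Non-improvers reaching 22 weeks | ≥22 weeks | <22 weeks | Rejection |
|---|---|---|---|
| 40% (32) | 144/176 = 81.8% | 176/224 = 78.6% | 13% |
| 35% (28) | 144/172 = 83.7% | 176/228 = 77.2% | 37% |
| 30% (24) | 144/168 = 85.7% | 176/232 = 75.9% | 69% |

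Check of the last row: SE = √[0.8 × 0.2 × (1/168 + 1/232)] = 0.0405; 0.0985/0.0405 = 2.43; P(Z > 1.96 − 2.43) is about 68%. With 200 women, rejection is 8/21/41%. With equal continuation it is 5%.

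**End date of continuing users.** The CRF holds only a start date for them (protocol 7.2.4.5), and the 6-month evaluation is recommended while no visit is mandated (protocol 7.2.4, 7.1). Without it such a woman is classed at about 3 months, yet AEs for a further 28 days count: 1 − exp(−0.02 × 3.92) = 7.5% against 5.8%, where 3.92 = 3 + 28/30.44. This is a smaller limitation.

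**The case against.** The tests are exploratory, with no decision rule, in a mainly descriptive study. Every rate above is assumed, and rejection runs from 4% to 100%. With 25–50% of AEs stopping treatment and 1–2% AEs per month, the base case gives only 4–22%. Protocol 7.9 says the SAP follows the regulator's re-examination guidelines, which may ask for tests by duration. The 3- and 6-month effectiveness tables are already planned: "The frequency and percentage of clinical response evaluation at 3 months (± 2 weeks), 6 months (± 2 weeks), last visit". Relabelling the rows as exposure, with a caution, might be enough.

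Much of this stands as a limit on size. The large AE figures need few or most AEs to stop treatment, and counting the 28-day window lowers most of them. Cancellation at 50% is not general either: rejection there is 19% with front-loaded AEs and 22% with 60% followed to 6 months. The effectiveness model fits vasomotor symptoms. For osteoporosis prevention the rating rests on test results, no scenario was modelled, and the documents do not say how it relates to continuing. If responders stopped more often, the bias would reverse.

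None of this makes the two items baseline factors. A caution beside a planned p-value leaves the misleading p-value in place, and the planned 6-month table covers continuers only. Whether the guidelines require these tests cannot be settled from these documents.

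**Conclusion.** The concern holds and should be fixed. As written, the SAP tests two follow-up variables as baseline factors, and with no true duration effect the tests can reject well above 5%. The AE error can take either sign, depending on how often AEs stop treatment and on follow-up. The effectiveness error plausibly favours long-term use: an apparent difference of 3 to 10 percentage points in the scenarios shown, conditional on non-improvers continuing less often. The mechanism follows from the documents; the sizes follow from assumed rates. Harm is confined to these two rows and how they are read against the second objective. Overall AE incidence and overall effectiveness rates do not change.

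**What to change.** 1. Remove both duration rows from the tests in SAP 8.2.1.3 and 8.2.2. Keep them as descriptive exposure data: counts and percentages, no p-values.
2. Report first-AE incidence per person-time by period since first dose (0–3, 3–6, >6 months), showing events and person-time, without a test. Censor events and person-time alike: continuing users at the last effectiveness evaluation; women who stop at last dose plus 28 days, or at withdrawal if earlier. Count separately any continuing user with no evaluation date. AEs after censoring stay in the overall tables. For partial onset dates, show the rates with the earliest and latest possible day, as a stated exception to SAP 7.
3. Show the 3- and 6-month ratings in the women who have both, and label the all-available 6-month rate as covering continuers only. In the 30% scenario the all-available rates read 80.0% then 85.7% with nobody changing; in the 168 women with both they are 85.7% and 85.7%.
4. Define the categories in days on one month convention: 22 weeks is 154 days, or 6 × 28 − 14, while the 6-month cut has no stated month length. This is labelling, not bias.
5. State the end-date rule for continuing users as a limitation.

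Person-time by final duration group would not repair item 2. In the related model it gave rate ratios of 0.15–0.75 with no true effect when 25–75% of AEs stopped treatment, whereas splitting each woman's own follow-up at 22 weeks gave 0.99–1.01. Under the proposed censoring with equal hazards, the 0–3 and 3–6 month rates were both 2.0 per 100 person-months at 2%. When risk differs between women (gamma variance 4), the first-AE rate falls anyway, from 1.8 to 1.5 at 2% and from 4.0 to 2.7 at 5%. Hence no test, and a note saying so.

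The cost is SAP wording and a little programming on dates already recorded, and two exploratory p-value rows lost per endpoint. The sponsor should confirm what the guidelines require; counts and percentages by duration remain. A note may be needed if periodic reports already carried these tests. The >6-month period may be nearly empty: about 22 person-months, so 22 × 0.02 = 0.4 events at 2% per month, if follow-up ends at 6 months (± 2 weeks).

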7.2.4.4. Concomitant Medications

Any concomitant medications should be recorded on the CRF for each subject together with the name of the drug, daily dose (unit), route of administration, duration of the treatment and purpose of the treatment.

7.2.4.5. Status of Administration of Duavive Tab.

The following will be recorded on the CRF for each subject:

- Treatment period: Record the start date and discontinuation date of the treatment. If the medication is being continued at the completion of the study, record the start date only and check 'Medication is continued'.
- Daily dose: Select 0.45 mg/20 mg or 'Other'. If 'Other' is selected, record the daily dose.

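### Concomitant medication is tested as a baseline factor for adverse events, but drugs given to treat an adverse event are recorded in the same CRF section, so the event can create the exposure

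*SAP*

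**What the plan says.** SAP 8.2.1.1 opens its list with "Baseline characteristics for this study are defined as follows" and includes "Concomitant medication (Yes, No") among the categorized items. It gives no rule on when a drug must have been taken or why.

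SAP 8.2.1.3 uses that whole list for safety: "Adverse event presentations will be split by the following baseline characteristics (See Categorized measurements of Section 8.2.1.1"). The proportion of women with an AE is "compared between subcategories of each baseline characteristic using chi-square test or Fisher's exact test". SAP 8.1 sets a two-sided 0.05 level.

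The data behind the variable come from Protocol 7.2.4.4: "Any concomitant medications should be recorded on the CRF for each subject together with the name of the drug", along with dose, route, "duration of the treatment and purpose of the treatment". The section has no reference to the first dose. Protocol 7.3.1.1, under other measures taken for an AE, adds: "Prescription of treatment drug (Record the details in the Concomitant Medications section"). The severity scale in that section also anticipates drug treatment of AEs. A moderate event is described partly by this: "Dose of the medicinal product is adjusted or other therapy is added due to the AE".

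**The concern.** A baseline factor should be fixed before the outcome can occur. Here one CRF section holds both drugs already in use at the first dose and drugs prescribed because of an AE, and the SAP reduces it to Yes or No. Take two women on no other drug. One has an AE that is treated with a drug and is counted as Yes; the other has no AE and stays No. The outcome has defined the exposure.

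Objective 2 is to identify factors that affect safety and efficacy, and these subgroup tests are the planned means. No adjusted model follows that might expose the artefact. SAP section 3 does not exempt the table from the interim analyses, so it would appear in the periodic reports as well as the re-examination report. The risk is a statement that co-medicated women have more AEs when the difference comes from how the variable was built.

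**Working it through.** **Figure to reproduce.** There is none. Protocol 7.5 says a sample size calculation does not apply, and the documents give no AE rate, treated share or background medication use.

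**Inputs.** N = 600 (the enrolment minimum, Protocol 7.5). Three quantities are assumptions:
- p: proportion of women with an AE
- c: proportion using another drug at first dose, taken as independent of AE occurrence (no true effect)
- t: share of women with an AE who are given a drug for it

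**Formulas.** If any entry in the section counts as Yes:
- P(Yes | AE) = c + (1 − c)t, and P(Yes | no AE) = c
- AE rate in Yes = p[c + (1 − c)t] / [c + (1 − c)pt]
- AE rate in No = p(1 − t) / (1 − pt)
- Spurious odds ratio = [c + (1 − c)t] / [c(1 − t)]

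The odds ratio exceeds 1 for every t > 0 with 0 < c < 1, so the direction does not depend on the assumptions.

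**Worked case: p = 0.20, t = 0.30, c = 0.50**
- Yes: 0.20 × 0.65 / (0.50 + 0.50 × 0.06) = 0.13 / 0.53 = 24.5%
- No: 0.20 × 0.70 / (1 − 0.06) = 0.14 / 0.94 = 14.9%
- Odds ratio: 0.65 / 0.35 = 1.86

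**Range.** The p-value is from an uncorrected chi-square test on the expected table, n = 600.

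| p | t | c | AE rate, Yes | AE rate, No | Difference (points) | p-value |
|---|---|---|---|---|---|---|
| 5% | 5% | 80% | 5.1% | 4.8% | 0.3 | 0.89 |
| 10% | 10% | 60% | 10.6% | 9.1% | 1.5 | 0.55 |
| 20% | 15% | 60% | 21.6% | 17.5% | 4.0 | 0.23 |
| 20% | 30% | 50% | 24.5% | 14.9% | 9.6 | 0.003 |
| 20% | 50% | 30% | 35.1% | 11.1% | 24.0 | about 1e-12 |
| 30% | 75% | 30% | 54.1% | 9.7% | 44.4 | below 1e-12 |

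**How often the test would mislead.** This depends on the grid chosen:
- p 10/20/30%, t 25/50/75%, c 30/60%: 17 of 18 expected tables have p < 0.05.
- p 5/10/20%, t 5/10/15/20/25%, c 30/60/80%: 7 of 45 do.

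**Simulation.** The SAP's chi-square/Fisher rule was run 2,000 times per scenario, with p 5-30%, c 30-70% and t 10-50%. The false-positive rate was 0.847 in the worked case (formula 0.842) and 0.064 in the mildest case (p = 0.05, c = 0.7, t = 0.1; formula 0.049). It reached 1.00 in the most extreme cases. With Yes limited to drugs in use at first dose, the rate was 0.037 to 0.062 in all scenarios, in line with the nominal 0.05.

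**The case against.** **Baseline already means at first dose.** This is the natural defence, but the list does not bear it out. It also holds total administration period and long-term administration, which are known only after baseline. Where the authors meant a time point they gave one: prior hormone therapy is worded as before Duavive in the same list, and Protocol 7.2.4.2 ties past and present disease to the first dose. A programmer following the text could code any entry as Yes.

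**The tests are exploratory.** This stands and limits the severity. SAP section 4 marks hypotheses and decision rules as not applicable, and Protocol 7.7.2 makes AE frequency the primary concern and relies mainly on descriptive statistics. One factor among about twelve is affected.

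**The size is unknown.** This also stands. Protocol 7.3.1.1 offers untreated as an option, so the treated share may be low.

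**Type of concomitant medications.** SAP section 3 implies an output on this for the final report. It may show readers that AE-treatment drugs are included, but it does not correct the test.

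A reader might infer three stronger things that the documents do not support:
- *The factor will come out significant.* That depends on the assumed treated share and background use, as the two grids show.
- *The effectiveness split in SAP 8.2.2 is biased in the same way.* It uses the same undefined variable, but neither document describes a drug given for lack of response being entered in this section. The circular route is documented for AEs only.
- *Medication is the only item without a baseline anchor.* The two administration-period items show otherwise.

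**Conclusion.** The concern holds for the AE comparison in SAP 8.2.1.3. As written, an AE treated with a drug can turn a woman from No to Yes. Whenever this happens in a woman on no other drug, it pushes the comparison towards a spurious excess of AEs in Yes. That direction follows from the definitions.

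The size rests entirely on the three assumed quantities. It runs from a difference too small to notice to one that would dominate the table, and the documents give no basis for choosing within that range.

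This should be fixed, but it does not threaten the study's main output. Overall AE incidence and its confidence interval, the preferred-term tables, and the serious and unexpected AE tables do not use this variable. What is at risk is one exploratory risk-factor result under objective 2.

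**What to change.** In SAP 8.2.1.1:
- Define the tested factor as concomitant medication in use at the first Duavive dose (Yes, No, Unknown).
- As a minimum, always exclude any drug whose recorded purpose, or whose entry under the AE's other measures, shows it was given to treat an AE.
- Use Unknown where timing cannot be derived from the recorded duration. Add a matching exception to SAP section 7, which otherwise drops missing or incomplete dates.
- Keep all concomitant medication as a descriptive table without a test.

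**Cost.** SAP wording and one derivation. Purpose and duration are already collected under Protocol 7.2.4.4, so excluding AE-treatment drugs needs no new data item. The first-dose restriction is less certain: that section names duration rather than a start date, whereas Protocol 7.2.4.5 asks for the start and discontinuation dates of Duavive itself. The restriction therefore works only where a start date can be derived, and some women will fall in Unknown. Co-medication begun after the first dose but before any AE would no longer count in the tested factor. That is a real exposure given up in return for a clean comparison.
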